7.1.2.5. Serum β 2-microglobulin

One blood sample for β 2-microglobulin will be collected and tested by local laboratory at C1D1 and Cycle 10 for subjects in the FD Cohort (see [Appendix B](#)).

7.1.2.6. Pregnancy Test

Serum pregnancy test will be required at Screening by local laboratory only for women of childbearing potential. A urine pregnancy test will also be performed on Day 1 prior to first dose. If positive, pregnancy must be ruled out by ultrasound to be eligible. This test may be performed more frequently if required by local regulatory authorities.

7.1.3. Diagnostics/Procedures

7.1.3.1. ECG

Electrocardiograms should be performed at the investigator's discretion, particularly in subjects with arrhythmic symptoms (eg, palpitations, lightheadedness) or new onset dyspnea.

During visits in which both ECGs and blood draws are performed, ECGs should be performed first.

At Screening, and if clinically indicated during the conduct of the study, 12-lead ECG will be done *in triplicate* (≥ 1 minute apart) in supine position after resting at least 10 minutes.

Abnormalities noted at Screening should be included in the medical history.

7.1.3.2. CT/MRI

CT scans of the neck, chest, abdomen and pelvis will be performed throughout the study until disease progression is confirmed. MRI may be used to evaluate sites of disease that cannot be adequately imaged using CT (in cases where MRI is desirable, the MRI must be obtained at baseline and at all subsequent response evaluations). If MRI is required for any other reason, this must first be discussed with the study Medical Monitor.

De-identified copies of all imaging will be submitted to the Sponsor or designee.

7.1.3.3. Bone Marrow Biopsies and Aspirate

Bone marrow biopsy and aspirate samples will be assessed locally and used for disease assessment by Investigator, to confirm complete response, to confirm cytopenic progression attributable to CLL, and distinguish autoimmune and treatment-related cytopenias. Bone marrow components should be evaluated for complete response per 2008 IWCLL criteria including relative cellularity for patient's age, % lymphocytes, and for the presence of B lymphoid nodules.

In the MRD cohort: Bone marrow aspirate will be used for MRD assessment by central lab flow cytometry at C16D1 and visits with CR assessments. A Cycle 29 bone marrow aspirate should be obtained to confirm ongoing MRD-negativity or attainment of new MRD-negativity (see below for additional details).

In the Fixed Duration cohort: Bone marrow aspirate will be used for MRD assessment by central lab flow cytometry at the following: C10D1, visits with CR assessments, and the C19D1 assessment (3-months after the completion of Cycle 15) (see below for additional details).

Table 8. Overall Response Assessment

	BM Biopsy	BM Aspirate	Peripheral Blood
Clinical response (or progression when appropriate)	X (and at select cycles – see Table 9 and Table 10)	X (any time a BM biopsy is collected to confirm CR, also collect an aspirate for MRD)	X
MRD		X (at select cycles, see Table 11 and Table 12)	X (at select cycles, see Table 11 and Table 12)

Table 9. MRD cohort: Bone Marrow Biopsy and Aspirate Collection Times for Clinical Response

	Screening Visit	C16D1 Visit (± 14 days)	C29D1 Visit (± 14 days)	Suspected CR Visit	Suspected PD Visit
BM Biopsy (local lab and central lab)	X ^b	X ^{a,c,f}	X ^{a,f}	X ^{a,f}	X ^e
BM Aspirate (local and central lab)	X ^b	X ^{a,c,f}	X ^{a,d,f}	X ^{a,f}	X ^e

- BM biopsy and aspirate for clinical response assessment (local lab and ██████████ central lab); BM aspirate used for MRD assessment, and ██████████ studies (MRD central lab)
- Unless previously collected within 90 days prior and not needed for karyotype, a portion of BM biopsy and aspirate is forwarded to the central laboratory for assessment
- Unless collected prior and within 3 months for CR assessment, and confirmed CR and MRD-negative in BM
- Collected in randomized subjects, and in any subject w/ MRD-neg conversion in PB
- Only required to document PD by cytopenic progression, as appropriate (local lab)
- If the bone marrow biopsy and aspirate results demonstrate a hypocellular marrow, a repeat biopsy (in 4 weeks up to 6 months) is needed per IWCLL Guidelines (see Section 7.2.3.2)

Table 10. Fixed Duration cohort: Bone Marrow Biopsy and Aspirate Collection Times for Clinical Response

	Screening Visit	C10 (±14 days)	C19 (3 mo after completion of C15 combo [±14 days])	Suspected CR Visit	Suspected PD Visit
BM Biopsy (local and central lab)	X (local only)	X ^{a,c,d}	X ^{a,d}	X ^{a,d}	X ^b
BM Aspirate (local and central lab)		X ^{a,c,d}	X ^{a,d}	X ^{a,d}	X ^b

- BM biopsy and aspirate for clinical response assessment (local lab and ██████████ central lab); BM aspirate used for MRD assessment, and ██████████ studies (MRD central lab)
- Only required to document PD by cytopenic progression, as appropriate (local lab)
- Unless collected prior and within 3 months for CR assessment, and confirmed CR and MRD-negative in BM
- If the bone marrow biopsy and aspirate results demonstrate a hypocellular marrow, a repeat biopsy (in 4 weeks up to 6 months) is needed per IWCLL Guidelines (see Section 7.2.3.2)

At Screening (MRD and FD Cohorts)

A unilateral bone marrow biopsy must be obtained at Screening or up to 90 days before enrollment for disease confirmation.

The following material will be sent to the central laboratory:

- Bone marrow trephine (≥ 1 cm) in a container of neutral buffered formalin (no other fixative allowed); NOTE: The bone marrow trephine will be split in half with one portion to remain at the site for local assessment and the other half sent to the central laboratory
- Bone marrow aspirate

If insufficient marrow biopsy material or slides are available to be submitted, high resolution images of the available representative slides should be acquired and submitted instead.

Copies of redacted bone marrow pathology reports for samples reviewed locally will be collected and may be reviewed by the Sponsor and/or IRC.

For Response Evaluation (MRD and FD Cohorts)

At every Overall Response Assessment with a scheduled BM evaluation ([Table 9](#) for MRD cohort and [Table 10](#) for FD cohort), or if the subject's physical examination findings, laboratory evaluations, and radiographic evaluations suggest that CR has been achieved in all response parameters at other time points (Suspected CR), a bone marrow aspirate and biopsy must be obtained to confirm the CR and to evaluate minimal residual disease.

Bone marrow collected to confirm CR must have minimal residual disease (MRD) assessed by flow cytometry on the aspirate (see below for more details). In cases where cytopenic progression is suspected, the bone marrow aspirate or biopsy should be used to distinguish autoimmune and drug-related cytopenias.

The following material will be sent to the central laboratory:

- Bone marrow trephine (≥ 1 cm) in a container of neutral buffered formalin (no other fixative allowed) NOTE: The bone marrow trephine will be split in half with one portion to remain at the site for local assessment and the other half sent to the central laboratory
- Bone marrow aspirate

If insufficient marrow biopsy material or slides are available to be submitted, high resolution images of the available representative slides should be acquired and submitted instead.

Copies of redacted local bone marrow pathology reports for samples reviewed locally will be collected and may be reviewed by the Sponsor and/or IRC.

Quantitative Minimal Residual Disease (MRD) Assessment by Central lab

A C1D1 PB sample will be submitted for MRD evaluation to establish a baseline immunophenotypic profile. Starting from C7D1 on, MRD will be assessed by PB every 3-12 cycles. Refer to [Table 11](#) and [Table 12](#) for MRD sample collection schedule.

In the MRD Cohort:

A bone marrow aspirate will be collected from all subjects for assessment of MRD status at Cycle 16 (± 14 days) unless collected previously in those with a documented CR and MRD-neg confirmed in BM after the start of study treatment. An additional bone marrow aspirate should be collected at Cycle 29 (± 14 days) in randomized subjects, and in any subject with MRD-neg conversion in PB.

In subjects who consent, an additional bone marrow aspirate (after suspected CR or C16) can be collected prior to randomization to serially confirm MRD-negativity in the BM compartment.

Table 11. MRD Cohort: MRD Sample Collection Schedule

	C1D1	C7D1	C10D1	C13D1	C16D1 (± 14 days)	C20- C29D1 Q3 cycles (± 14 days)	C35D1 and Q6 cycles thereafter	To Confirm CR	To Confirm MRD+ Relapse	End of Treatment
BM Aspirate					X ^a	X (C29) _{a,b,c}		X		
Peripheral Blood	X	X	X	X	X	X	X	X	X	X

a. Unless collected prior for CR assessment, and were MRD-neg in BM

b. Collected in randomized subjects, and in any subject w/ MRD-neg conversion in PB

[figure not shown]
c. ± 14 day window applies to BM aspirate only

In the Fixed Duration Cohort:

A bone marrow aspirate will be collected from all subjects for assessment of MRD status at Cycle 10 and 3 months after the completion of Cycle 15 (ie, C19). Bone marrow assessments can be performed if needed to confirm CR.

Table 12. Fixed Duration Cohort: MRD Sample Collection Schedule

	C1D1	C7D1 (±14 days) ^a	C10D1 (±14 days) ^a	C13D1 (±14 days) ^a	EOT (within 30 days of last study drug; C17 for those who complete regimen)	C19D1, C25D1, C28D1, C31D1 and annually thereafter (±14 days) ^a
BM Aspirate		[X - if needed to confirm CR]	X	[X - if needed to confirm CR]		X C19D1
Peripheral Blood	X	X	X	X	X	X

Every 3-12 cycles^a 

a. ±14 day window applies to BM aspirate only

7.1.3.4. FISH Assays

Cytogenetic profiles will use CLL FISH probes to detect abnormalities in chromosomes 11q, 12, 13q, and 17p.

For all subjects, peripheral blood for FISH will be collected at C1D1 and at Day 1 of reintroduction of study drug.

7.1.3.5. Karyotype

Karyotype will be derived from PB (or BM aspirate - MRD Cohort only) using a stimulated culture method. BM aspirate will be used in lieu of PB when the ALC is ≤4000 in MRD cohort.

If a BM was collected within 90 days prior to screening and the ALC is ≤4000 then another BM aspirate will be required before C1D1 first dose and at Day 1 of reintroduction of study drug.

7.1.4. Pharmacokinetics

7.1.4.1. Pharmacokinetics – MRD Cohort Only

Pharmacokinetics of ibrutinib and its metabolite PCI-45227 will be determined at steady-state during the Pre-randomization Phase, single-agent ibrutinib (lead-in period) on Day 1 of Cycle 2 at time-points specified in Table 13 below in the MRD cohort only. Pharmacokinetics will not be assessed in the Fixed Duration cohort. Ibrutinib and venetoclax should be dosed together at the same time with 8 ounces of water and a meal. For subjects not able to swallow all ibrutinib capsules and venetoclax pills at the same time, administration should be completed as close together in time as possible. It is anticipated that steady state will be reached after 1 week of administration of the highest venetoclax dose (400 mg). Pharmacokinetic samples (PK) should only be collected when treatment has been without interruption for at least 7 days. In the case of treatment interruption, pharmacokinetic sampling should be delayed until completion of an

uninterrupted 7 days of dosing. In cases of dose reduction, pharmacokinetic sampling should be delayed until completion of an uninterrupted 7 days of consistent dosing.

Pharmacokinetics of ibrutinib and venetoclax when dosed in combination will be also determined at steady-state on Day 1 of Cycle 6 at time-points specified in [Table 13](#) below.

Table 13. Pharmacokinetic Sample Schedule for Ibrutinib and Venetoclax (MRD Cohort Only)

Study Drug PK	Cycle ^f	Day	Pre-dose PK ^c & Meal ^d	Study Drug Dose ^e	Time after ibrutinib or ibrutinib + venetoclax				
					1 hour (± 15 min)	2 hour (± 15 min)	4 hour (± 30 min)	6 hour (± 30 min)	8 hour (± 1 h)
Ibrutinib	2 ^a	1	X	X	X	X	X	X	X
Ibrutinib & Venetoclax	6 ^b	1	X	X	X	X	X	X	X

- Ibrutinib single-agent only steady-state PK
- Ibrutinib and venetoclax combination steady-state PK
- Predose samples should be collected 30 minutes prior to the administration of ibrutinib (lead-in period) or ibrutinib and venetoclax (combination period)
- The meal to be completed within 30 minutes
- Ibrutinib/venetoclax to be dosed 30 minutes after the start of the meal
- PK should only be drawn when ibrutinib (C2), and ibrutinib with venetoclax (C6) are at steady state plasma levels. If any dose of ibrutinib and/or venetoclax were withheld in the week prior to C2D1, and C6D1, then PK assessment should be rescheduled to the next study visit day after doses have been consistently administered for ≥1 week

Example:

Predose PK --7:00a
 Breakfast ----7:00a to 7:30a
 Dose -----7:30a
 1 hr PK -----8:30a
 2 hr PK -----9:30a
 4 hr PK -----11:30a
 6 hr PK -----1:30p
 8 hr PK -----3:30p

Refer to the laboratory binder for instructions on collecting and processing these samples. On the day of the sampling visit, the clinical staff will instruct the subject to not take a dose before arrival at the clinic. Study drug intake will be observed by clinic staff. The actual time (versus requested time) that each sample is drawn must be recorded using a 24-hour format. The same clock should be used for recording the time of dosing. In the event that medical management is needed during the PK collection period, administration of concomitant medications should be recorded.

Pharmacokinetics Sample Collection for Subjects Treated with a Concomitant CYP3A Inhibitor While on Ibrutinib and/or Venetoclax Treatment

For subjects who must start a moderate or strong CYP3A inhibitor while on treatment with ibrutinib and/or venetoclax, additional PK blood samples for evaluation of ibrutinib and/or venetoclax exposure are requested approximately one week post-initiation of concomitant CYP3A inhibitor. PK samples will be collected at:

- Pre-dose (If possible, sample should be obtained 22-24 hours post the previous day's dose and before dosing on the day of the scheduled visit)
- 1 hour \pm 15 min
- 2 hours \pm 15 min
- 4 hours \pm 30 min
- 6 hours \pm 30 min
- 8 hours \pm 1 h

7.1.4.2. [REDACTED]

[REDACTED]

7.1.4.3. [REDACTED]

[REDACTED]

7.1.4.4. [REDACTED]

[REDACTED]

7.2. Efficacy Evaluations

Clinical disease evaluations will include:

- Physical examination (which will focus on the presence/absence of size increase/decrease in lymph nodes, liver, and spleen)
- Hematologic parameters by CBC performed at a local laboratory
- Radiographic evaluation (CT or MRI scan of the neck, chest, abdomen, and pelvis)
- Bone marrow biopsy (as appropriate) if there is evidence of CR in the other response parameters

If study drug is held before a scheduled clinical response assessment, then the response assessment can be delayed up to 4 weeks to allow re-initiation of study drug for 2 weeks (or as long as possible) prior to performing scheduled response assessment.

Clinical efficacy assessments, for the purpose of the study result analyses, will be performed by Investigators. For response assessments not requiring a CT scan, the Investigator should evaluate response based on available clinical data, including physical examination and laboratory results. For the MRD and Fixed Duration cohorts, imaging will be collected and stored centrally. The Sponsor may utilize IRC for independent review of efficacy with details to be outlined in the separate IRC charter.

MRD Evaluations:

Samples for MRD analysis will be sent to a central laboratory that has a validated flow cytometry assay that has a limit of detection of 10^{-4} . MRD will be assessed in the following compartments:

- Bone marrow
- Peripheral blood

7.2.1. Definitions

7.2.1.1. Measurable Disease

Subjects must have at least 1 measurable site of disease to participate in this study. Measurable sites of disease are defined as lymph nodes, or lymph node masses. A measurable site of disease must be greater than 1.5 cm in the longest diameter. Measurement must be determined by imaging evaluation.

Tumor lesions that are situated in a previously irradiated area might or might not be considered measurable. If there are tumor lesions in previously irradiated areas and progression has occurred, these lesions will be considered measurable. If tumor lesions in previously irradiated areas are present and have been stable, then these lesions are not considered measurable. If tumor lesions in previously irradiated areas progress during the study, then disease progression will be considered as having occurred provided progression is confirmed by the Investigator.

All other sites of disease will be considered assessable. Assessable disease includes objective evidence of disease that is identified by radiological imaging, physical examination, or other procedures, as necessary, including peripheral blood counts.

7.2.1.2. Treatment-Related Lymphocytosis

Treatment-related lymphocytosis, for the purposes of this protocol, is defined as an elevation in blood lymphocyte count of $\geq 50\%$ compared to baseline and $\geq 5000/\mu\text{L}$ that occurs in the setting of unequivocal improvement in at least one other disease-related parameter including lymph node size, spleen size, hematologic parameters (hemoglobin or platelet count), or disease-related symptoms. Given the known mechanism of action of BCR-inhibiting agents including ibrutinib, treatment-related lymphocytosis is an expected and frequent pharmacodynamic phenomenon observed with initiation (or re-initiation) of ibrutinib.

Response assessment in CLL subjects treated with novel agents has been clarified by the authors of the IWCLL 2008 guidelines and is outlined in the [NCCN NHL 2016](#) guidelines, supporting that subjects with isolated lymphocytosis in the setting of improvement in other disease parameters should not be considered to have clinical progressive disease or treatment failure ([Cheson 2012](#)).

7.2.1.3. Richter's Transformation

Richter's syndrome (RS) is lymphomatous transformation to a more aggressive histology in a subject with CLL or SLL. RS is most often characterized by the development of high-grade NHL or Hodgkin's disease. Symptoms of Richter's transformation can include new or progressive lymphadenopathy or organomegaly, fever, loss of weight and muscle mass, and other health problems. Richter's transformation can be suggested by a CT/PET scan, but should be confirmed with a biopsy (eg, lymph node) demonstrating the histologic transformation.

7.2.1.4. Minimal Residual Disease (MRD)

MRD is a low-level of disease that persists, and which is not detectable with routine imaging nor routine laboratory tests, but can be demonstrated in PB or BM with more sensitive flow cytometry assays.

7.2.1.4.1. MRD-Negativity

MRD-negativity is defined as <1 CLL cell per 10,000 leukocytes ($<1 \times 10^{-4}$), as assessed by flow cytometry of a peripheral blood (PB) or bone marrow (BM) aspirate sample.

Confirmed MRD-negative response for randomization purposes requires MRD-negativity serially over at least 3 cycles, with negativity in both BM and PB. Subjects who do not achieve confirmed MRD-negative status are not considered to have a MRD-negative response for randomization purposes in the MRD cohort. See [Section 7.1.3.3](#) for MRD assessment schedule.

7.2.1.4.2. MRD-Positive Relapse (MRD Cohort Only)

MRD-positive relapse is defined as an increase in CLL cells ≥ 1 per 100 leukocytes ($\geq 1 \times 10^{-2}$) confirmed on two separate serial occasions, after a confirmed MRD-negative response, as assessed by flow cytometry of a PB or BM aspirate sample.

7.2.2. Guidelines for Clinical Disease Evaluation

Objective response will be categorized as CR, CR with incomplete bone marrow recovery (CRi), nodular partial response (nPR), partial response (PR), PR with lymphocytosis (PRL), stable disease (SD), or progressive disease (PD)—all based upon IWCLL criteria ([Hallek 2008](#), [Hallek 2012](#), [Hallek 2013](#), [Cheson 2012](#)). All responses must be maintained for at least 2 months to be considered confirmed. CRs must be confirmed by bone marrow biopsy/aspirate. Response assessments on treatment arms will occur independent of ongoing therapy. For purposes of this protocol, 2 months equals 2 cycles (56 days) with each cycle equaling 28 days.

Given the known mechanism of action of BCR-inhibiting agents, including ibrutinib, and the treatment-related lymphocytosis frequently observed during treatment with ibrutinib, isolated treatment-related lymphocytosis (in absence of other clinical, CT, or laboratory evidence of disease progression) will not be considered progressive disease. This approach is supported by

both the authors of the IWCLL 2008 and 2017 guidelines (Hallek 2012, Cheson 2012) and the NCCN.

The requirement for each parameter at baseline to be evaluable throughout the study is outlined in Table 14.

Table 14. Evaluable Parameter Requirements

Parameter	Requirements to be Evaluable for Response
Measurable Disease (required for all subjects)	Lymph Node >1.5cm
Splenomegaly	Enlarged spleen
Hepatomegaly	Enlarged liver
Absolute Lymphocyte Count (ALC)	≥4,000/μL
Platelets	≤100,000/μL
Absolute Neutrophil Count (ANC)	≤1500/μL
Hemoglobin	≤11.0 g/dL

7.2.3. Clinical Response Categories

Investigator assessment of response should include physical examination, radiographic imaging, and evaluation of blood and marrow (if applicable). For response assessments not requiring a CT scan, the Investigator should evaluate response based on available clinical data, including physical examinations and laboratory results. Definition of response for CR, CRi, nPR, PR, PRL and disease progression will be evaluated by the criteria listed in Table 15. Group A criteria define the tumor load and Group B criteria define the function of the hematopoietic system. Response must be confirmed by CT when available, and must last at least 2 months without transfusional support or growth factor product to be considered a confirmed response.

7.2.3.1. Complete Response (CR)

All of the following are required for a CR:

- No significant lymphadenopathy (>1.5cm) palpable on examination or by CT
- No hepatosplenomegaly on examination or by CT
- No constitutional symptoms (ie, no fever >38°C for ≥2 weeks, no ongoing unintentional ≥10% body weight loss, no night sweats for >1 month without other evidence of infection, no fatigue interfering with work or usual activities) attributable to CLL.
- Neutrophils >1500/μL, platelets >100,000/μL, and Hgb >11g/dL without recent growth factor or transfusions
- ALC <4,000/μL

Marrow aspirate and biopsy must be performed after all other criteria meet the definition of CR. To define a CR, the marrow sample must be at least normocellular for age, with less than 30% of nucleated cells being lymphocytes. B-lymphoid nodules should be absent.

In addition, in subjects with a CR, MRD should be performed on both peripheral blood and bone marrow aspirate to evaluate MRD status.

Table 15. Criteria for Clinical Response Categories

Parameter	CR	PR	PD
Group A			
Lymphadenopathy ^a	None; ≤1.5cm	Decrease ≥50%	increase ≥50%
Hepatomegaly	None	Decrease ≥50%	increase ≥50% or new hepatomegaly
Splenomegaly	None	Decrease ≥50%	increase ≥50% or new splenomegaly
Blood lymphocytes	<4000/μL	Decrease ≥50% from baseline	increase ≥50% over baseline ^c
Marrow ^b	Normocellular, <30% lymphocytes, no B lymphoid nodules. Hypocellular defines CRi ^d in a patient with cytopenias		
Group B			
Platelet count	>100,000/μL	>100,000/μL or increase ≥50% over baseline	Decrease of ≥50% from baseline secondary to CLL
Hemoglobin	>11 g/dL	>11 g/dL or increase ≥50% over baseline	Decrease of >2g/dL from baseline secondary to CLL
Neutrophils	>1500/μL	>1500/μL or increase ≥50% over baseline	N/A

- Sum of the products of multiple lymph nodes (as evaluated by CT scans) or the longest diameter of one target lymph node
- This parameter is not relevant for the PD category unless confirming cytopenic progression.
- Subjects with treatment-related lymphocytosis should remain on study treatment in the absence of other criteria for progressive disease (see [Section 7.2.1.2](#)).
- Hypocellular marrow is a CRi when peripheral blood cytopenias not meeting Group B criteria are present. CRi requires at least one abnormal Group B criteria.

Note: Group A defines the tumor load and Group B defines the function of the hematopoietic system

CR: all of the criteria need to be met and subjects have to lack disease related constitutional symptoms.

Bone marrow and aspirate is required to confirm CR.

PR: At least two of the Group A parameters must be met; with two exceptions: 1) subjects who only have abnormal lymph nodes at baseline, or 2) subjects who have only abnormal lymph node and abnormal lymphocyte count (ALC) at baseline. For these two exceptions, subjects will only need to meet the lymph node response criteria.

In addition to the Group A criteria, all subjects must also have a response in at least one of the Group B criteria.

SD: the absence of PD and the failure to achieve a response.

PD: at least 1 of the above criteria from Group A or B are met or development of transformation to a more aggressive histology

Cross reference: [Hallek 2008](#), [Hallek et al. June 2012 e-letter](#), [Hallek 2013](#)

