7.2.3.2. Complete Response with an Incomplete Marrow Recovery (CRi)

Complete response with an incomplete marrow recovery (CRi) is defined as a CR with an incomplete recovery of the subject's bone marrow, manifested by persistent cytopenias. Subjects who have a CRi fulfill all criteria for a CR, but continue to have persistent anemia, thrombocytopenia, or neutropenia. These cytopenias are due to drug toxicity in the bone marrow and are not due to any evidence of CLL. If the marrow is hypocellular, a repeat determination should be performed after 4 weeks, or when peripheral blood counts have recovered. However, this time interval should not exceed 6 months.

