### **FD Cohort**

The primary hypothesis of this cohort is that: Complete response rate (CRR) is  $> 37\%$  after 12-cycle Ibr + Ven treatment.

The statistical hypotheses are as follows:

$$H_0: \text{CRR} \leq 37\%$$

versus

$$H_1: \text{CRR} > 37\%$$

These hypotheses will be tested at 1-sided  $\alpha$  level of 0.025 using asymptotic test for the binomial proportion. Since the assumption for sample size and power of this cohort is based on the historical data of subjects without del 17p, the formal hypothesis testing will be performed on the non-del 17p population (section 2).

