## FD Cohort

In the FD cohort, assuming the complete response rate for Ibr + Ven is 50%, 125 subjects without del 17p will provide 83% power to ensure the rate is > 37% at 1-side alpha 0.025. A CR rate of 50% would represent meaningful improvement compared to the CR rate seen with the fixed duration combination of bendamustine + rituximab (31%), and would be an improvement over the CR rate seen with the standard of care fixed duration regimen fludarabine, cyclophosphamide and rituximab (40%) which were obtained in the CLL10 study, which included only patients without del 17p (Eichhorst 2016).

The sample size and power calculations were calculated using the software package, East (Cytel Software Corp, Cambridge, MA) version 6.3.

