Complete response rate (CRR)	The proportion of subjects achieving a best overall response of CR or CRi on or prior to initiation of subsequent antineoplastic therapy or, if applicable, reintroduction of study treatment, whichever occurs earlier.	
Primary The point estimate of CRR per investigator assessment and the corresponding 95% CI based on normal approximation to the binomial distribution will be provided. In FD cohort non-del17p population, p value for testing <math>CRR \leq 37\%</math> vs <math>CRR > 37\%</math> using asymptotic test for the binomial proportion will be calculated.
 
Sensitivity CRR per IRC assessment.
 
Supportive 1. Duration of complete response (DOCR defined as the interval between the date of initial CR or CRi until disease progression or death from any cause, whichever occurs first.) for subjects who achieved CR or CRi. 2. Durable CRR (defined as proportion of subjects with DOCR <math>\geq</math> 336 days (12 cycles))
 
Subgroup (defined in table 1) The point estimate of CRR per investigator assessment and its 95% CI by normal approximation to the binomial distribution for each subgroup.

Secondary Endpoints for MRD and FD Cohorts		
Overall response rate (ORR)	The proportion of subjects achieving a best overall response of CR, CRi, nPR, or PR on or prior to initiation of subsequent antineoplastic therapy or, if applicable, reintroduction of study treatment, whichever occurs earlier.	
Primary The point estimate of ORR per investigator assessment and the corresponding 95% CI based on normal approximation to the binomial distribution will be provided.
 
Sensitivity ORR per IRC assessment.

Duration of response (DOR)	Duration of response will be calculated for the subjects achieving a response (CR, CRi, nPR, PR) per investigator assessment and is defined as time from the date of initial response including PR with lymphocytosis to the date of disease progression or the date of death from any cause, whichever occurs first. For subjects without documented PD or death, DOR was censored at the date of last adequate disease assessment.	
Primary Kaplan-Meier estimates of median DOR time per investigator assessment and landmark estimates with 2-sided 95% CIs.
 
Sensitivity DOR per IRC assessment

Endpoint	Definition	Analysis Method

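### The FD primary CR/CRi rate is defined without the protocol's own 2-month confirmation rule, so an unmaintained response can count as a success in the test against 37%

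*Protocol*

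**What the plan says.** **Confirmation.** Protocol 7.2.2 requires every response to be maintained for 2 months to be called confirmed, and sets 2 months equal to 2 cycles, or 56 days. Protocol 7.2.3 repeats the rule with a condition: the response "must last at least 2 months without transfusional support or growth factor product to be considered a confirmed response".

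**Primary endpoint of the FD cohort.** Protocol 10.4.4 defines the complete response rate (CRR) as the share of subjects who reach CR or CRi by investigator assessment, and does not mention confirmation. SAP Table 2 defines it as "The proportion of subjects achieving a best overall response of CR or CRi on or prior to initiation of subsequent antineoplastic therapy" or reintroduction of study treatment, again without mentioning confirmation. The rate is tested against 37% "using asymptotic test for the binomial proportion" at 1-sided 0.025 in subjects without del 17p (SAP 1.3). SAP Table 2 adds CRR by the independent review committee (IRC) as a sensitivity analysis. Duration of complete response (DOCR) and durable CRR (DOCR of at least 336 days) are supportive. SAP section 6 lists one change of terminology and nothing on confirmation.

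**CR and CRi.** For CR, protocol 7.2.3.1 says "the marrow sample must be at least normocellular for age, with less than 30% of nucleated cells being lymphocytes". Table 15 footnote d says "Hypocellular marrow is a CRi when peripheral blood cytopenias not meeting Group B criteria are present. CRi requires at least one abnormal Group B criteria". Protocol 7.2.3.2 says "Subjects who have a CRi fulfill all criteria for a CR, but continue to have persistent anemia, thrombocytopenia, or neutropenia". Section 7.2.3.2 and Table 10 footnote d also call for a repeat marrow, between 4 weeks and 6 months later, when the marrow is hypocellular.

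**The concern.** The protocol has a rule for when a response is confirmed, but neither definition of the FD primary endpoint says whether it applies. Elsewhere, where confirmation is meant, the definition says so: MRD-positive relapse in protocol 7.2.1.4.2 and SAP Table 2 footnote 1 must be confirmed on two occasions. Read as written, CRR therefore counts a CR or CRi seen once and lost before 56 days, or one supported by transfusion or growth factor within that time.

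This is the only hypothesis test in the FD cohort. It is a single open-label arm, assessed by the investigator, against a fixed rate. There is no concurrent arm in which the same leniency would cancel out. Any response counted that the protocol would not call confirmed moves the result in one direction, towards success.

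**Working it through.** **Inputs.** From SAP 1.4: "125 subjects without del 17p will provide 83% power to ensure the rate is > 37% at 1-side alpha 0.025", and "assuming the complete response rate for Ibr + Ven is 50" per cent. So n = 125, p0 = 0.37, p1 = 0.50, z = 1.96.

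**1. The plan's own figure.** With the variance taken at p1:
- SE = √(0.50 × 0.50 / 125) = 0.0447
- (0.50 − 0.37) / 0.0447 − 1.96 = 0.947
- Power = Φ(0.947) = 82.8%, which is the stated 83%.

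With the null variance (SE 0.0432) the power is 84.5%. The exact rule (58 or more) gives 81.4%. The sample size statement is sound.

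**2. Boundary.**
- Null variance: 57/125 = 0.456, and (0.456 − 0.37) / 0.0432 = 1.99, which rejects. 56/125 gives 1.81, which does not.
- Sample variance: 58/125 = 0.464, and 0.094 / 0.0446 = 2.11, which rejects. 57/125 gives 1.93, which does not.

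The boundary is therefore 57 or 58. One subject is 1/125 = 0.8 points. At a 50% rate 62.5 responders are expected, which is 5.5 or 4.5 above the boundary.

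**3. What unconfirmed responses could do.** The documents give no frequency, so the ranges below are assumptions. They use the null-variance approximation, power = Φ[(p − 0.37 − 1.96 × 0.0432) / √(p(1 − p)/125)].

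Suppose the confirmed rate is exactly 37%, but unconfirmed responses raise the counted rate:

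| Counted rate | Chance of success | Exact, rule of 57 or more |
|---|---|---|
| 38% | 4.3% | 5.0% |
| 39% | 6.9% | 7.9% |
| 40% | 10.6% | 11.8% |

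The nominal level is 2.5%; the exact level of the rule of 57 or more, with no inflation, is 3.0%.

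Suppose instead that the any-time rate is 50% and a share of those responses fails confirmation. The power of a confirmed endpoint is then:

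| Share failing | Confirmed rate | Power |
|---|---|---|
| 0% | 50% | 84.5% |
| 5% | 47.5% | 67.6% |
| 10% | 45% | 45.8% |
| 15% | 42.5% | 25.1% |
| 20% | 40% | 10.6% |

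The first table shows what the present definition risks. The second shows what the stricter one could cost.

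**4. The CRi passages side by side.** Take a subject who meets every other CR criterion and has no CLL in the marrow.

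| Marrow | Counts | Table 15 and footnote d | 7.2.3.2 |
|---|---|---|---|
| Hypocellular | Low | CRi | CRi, on the low counts |
| Normocellular | Low from drug | Not provided for | CRi |
| Hypocellular on repeat | Recovered | Neither CR nor CRi | No category given |

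Both sources require a cytopenia for CRi. They differ on whether a hypocellular marrow is also needed, and neither settles the last row. The 7.2.3.2 column also assumes that its reference to all CR criteria excepts counts and cellularity. Read literally it could not be met, because the CR criteria include count thresholds.

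**The case against.** The best defence is that the SAP is silent rather than permissive. Sections 7.2.2 and 7.2.3 still govern how investigators assess response, SAP 1.1 ties assessments to IWCLL criteria, and section 6 declares no departure. Short-lived responses would show in DOCR and durable CRR, and the IRC gives a second reading. Near the planned 50% rate a few subjects would not matter.

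Much of this stands, and it rules out several stronger readings:
- A reader might infer that the SAP dropped a protocol requirement. It did not. Protocol 10.4.4 already omits confirmation and the SAP carries that forward, so the mismatch starts inside the protocol.
- A reader might infer that the problem would be invisible in the results. DOCR and durable CRR are prespecified and would reveal short responses.
- A reader might infer that some particular small number of reclassified subjects would decide the trial. No document supports such a number.
- A reader might infer from footnote d that cytopenic subjects generally score better than recovered ones. The mandated repeat marrow can turn a recovered case into CR, so the gap is limited to marrows still hypocellular on repeat. That such a subject becomes a PR is deduced by elimination, not stated.
- A reader might want CRi widened to hypocellular marrow without cytopenias. Footnote d and 7.2.3.2 both require cytopenias, and widening would loosen a single-arm endpoint. It is a preference, not a correction.

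What does not stand is the view that silence is enough. Two programmers could derive different responder counts from the same data, and each could cite the documents. Durable CRR uses 336 days, not 56, and does not alter the primary p-value. The documents also do not say whether the historical 31% and 40% rates were confirmed responses, which is a reason to report both versions.

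**Conclusion.** The concern holds for confirmation. As written, the FD primary rate can include a CR or CRi that the protocol would not call confirmed, and this can only raise the count in a test whose boundary is 57 or 58 of 125. The number of affected subjects is not in the documents, so neither the direction of a changed decision nor its probability can be stated; the rates in the tables are assumed. The arithmetic takes 125 evaluable subjects without del 17p. The sample size and the 83% power are not in error.

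The CR/CRi wording is a separate and minor matter: an incomplete cross-definition affecting an unknown and probably narrow group. It acts against success where a recovered case is left unclassified. Its net effect together with the confirmation issue cannot be computed.

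**What to change.** In protocol 10.4.4 and SAP Table 2, state that the primary CRR counts only CR or CRi meeting the protocol's own rule: maintained for at least 56 days, without transfusion or growth factor. Count a CR or CRi with no later adequate assessment (SAP Table 2 footnote 3 already defines adequate) as unconfirmed. Report any-time CR/CRi as a sensitivity analysis.

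Separately, reconcile Table 15, footnote d and 7.2.3.2 on two questions: whether CRi needs a hypocellular marrow, and how a marrow still hypocellular on the mandated repeat with recovered counts is classified. Give the investigators and the IRC the same text.

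**Cost.** Mainly wording and a re-derivation. Scheduled response visits at C7, C10, C13, C19, C25, C28 and C31 are 3 to 6 cycles apart (84 to 168 days), so the next visit falls beyond 56 days. The price is a slightly lower CRR and some loss of power, as in the second table. One practical limit is that protocol section 6 records concomitant therapy only to 30 days after the last dose, and the post-treatment visit list in 8.3.2 does not include it. The transfusion and growth-factor condition would therefore be harder to verify for responses first seen at C19 or later, and the SAP should say how such cases are handled.
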